6 ENDPOINTS AND COVARIATES

a. Primary Endpoint.

- **Primary endpoint 1:** Obtaining results / diagnosis of NGS and Ventana for the ALK biomarker.
- **Primary endpoint 1:** Analysis of NGS y Ventana for ALK.

b. Secondary Endpoints

Secondary endpoint 1: PE1 in prospective and retrospective patients.

Secondary endpoint 2: PE1 in smokers and non-smokers.

Secondary endpoint 3: PE1 depending on the location, stage and histological classification of the biopsy

Secondary endpoint 4: PE1 in patients of different gender and age.

6.1 EFFICACY/ EFFECTIVENESS ENDPOINT(S)

Not Applicable

6.2 SAFETY ENDPOINTS

Since NIRVANA X9001083 is a NI study without study drug and randomization procedures we are using the Adverse Event Report Form Completion Guide, for a Therapeutic Areas, For Investigators Conducting Pfizer-Sponsored Non-Interventional Clinical Studies, For Protocols with Stipulated Active Collection of Adverse Events (Including Pragmatic Clinical Studies [Non-Medicinal Intervention]) according CT24-GSOP-SD-GL25 version 4.0, effective date 01-Aug-2016.

6.3 OTHER ENDPOINTS

Establish the incidence of ROS1 alterations in South American populations
Assessment of inter-laboratory reliability of NGS methods to realized molecular diagnostics in cancer patients.

6.4 COVARIATES

a. Patient Strata.

The strata of the patient will be reported as a frequency count. The categories are Prospective Patients and Patients Retrospective. Smoker history

The smoking history will be reported as a categorical variable. The categories of smoker to consider are the following:

1. Never Smoker: No smoking exposure
2. Current Smoker: Currently uses tobacco in either cigarette, cigar or similar method (tobacco chewers excluded)
3. Former Smoker: Documented that the patient at one time smoked but then later quit. Covers instances where patients start smoking and then quit smoking multiple times. If a patient is a current smoker at the time of the study it will be considered as a “current smoker”
4. Smoking status unknown: For any patient that has no smoking status done.

b. Stage at diagnosis:

Stage will define at time of initial diagnosis of NSCLC and patients were staged according to the guidelines set by the NCCN version 7.2015. Patient stage will be categorized as:

1. STAGE O
2. STAGE 1A
3. STAGE 1B
4. STAGE 2A
5. STAGE 2B
6. STAGE 3A
7. STAGE 3B
8. STAGE 4

7 HANDLING OF MISSING VALUES

- **Clinical Data:**
 - Retrospective patients without information whether or not Smoker -> Patient is eliminated from the secondary analysis (of the smokers' subgroup).
 - Patients without PI data (the PI did not provide the information) -> Patient is removed from the secondary analysis (of the subset)
 - Patient without ALK data -> Patient is eliminated from primary analysis.
- **Sequencing:**
 - Insufficient sample: If at least 20 ug of DNA and 20 ug RNA or both are not obtained, the sample is eliminated from the primary analysis. The data will be used to establish pre-analytical QC parametric.
 - Samples within the sequencing flow: if BAM files have not been generated, the sample is eliminated from the primary analysis. For the final analysis just samples with BAM files will use to perform the genomic analysis, those samples without BAM files but that are not within the sequencing flow will be considered for the QC analytics.
- **Bioinformatics:**
 - Sample without cellularity, 100% cellularity will be assumed; the missing data will be recorded, the sample is included in all analyzes, except those where this variable is considered for QC analytics.
 - Sample without gender, UNK gender will be assumed (The team in case of UNK assumes as MALE), the missing data will be recorded, the sample is included in all analyzes. Except those where the subgroup is used for analysis.
 - DNA sample fails in QC parameters, it is eliminated from DNA dependent analysis, but it is included in primary analysis
 - RNA sample fails in QC parameters, primary analysis is eliminated.
- **** There are special cases where the primary analysis could be answered with defective samples, should it continue? Remove from the primary analysis, but group in special cases to analyze later.**

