2.1 STUDY DESIGN

This is a non-interventional study. This study NOT designated as a Post- Authorizations Safety Study (PASS).

[figure not shown]
2.1.1 General overview of the NIRVANA project.

This protocol use a primary source FFPE biopsies and clinical records obtained from patients recruited in clinical sites distributed in Chile, Brazil, and Peru. The FFPE is used to evaluate the ALK biomarker using either Vysis ALK Break Apart FISH test or the Ventana ALK IHC test and to perform the Next generation sequencing in nucleotides prepared from NSCLC FFPE blocks.

090177e191f145b5\Approved\Approved On: 25-Sep-2019 09:10 (GMT)

2.1.2 General overview of NGS test.

Prior to performing the NGS Test, the FFPE clinical specimens are prepared for pathology review. A microtome is used to prepare 5µm FFPE sections. A 5µm FFPE section is stained using a standard hematoxylin and eosin (H&E) protocol. Stained tissue sections are visually examined by a pathologist for confirmation of tumor content area, tumor content per tissue section (TC), region(s) of interest (ROI), ROI tumor content (ROI TC), and percent necrosis are all recorded on the case report form (as described in Protocol N° X9001083). If tumor content is greater than or equal to 20%, the tissue sections will be extracted. If tumor content is less than 20%, and ROI is greater than or equal to 10%, tumor areas will be macrodissected and enriched for tumor, in preparation for the extraction protocol.

Two sections will be extracted in order to meet minimum tissue input requirements. The tissue (with or without macrodissection) is taken through sample processing to isolate gDNA and total cell RNA. cDNA prepared from Total RNA is

The prepared DNA or cDNA sample is made into a library of amplicons using the Ion PGM Library Kit. Each sample is given a unique, identifying sequence by the addition of a nucleic acid barcode adapter. Using these barcode adapters up to 6 specimens (1 DNA library and 1 RNA library from each sample) each with its own unique barcode can be templated and sequenced in the same system run with DNA, RNA and 2 NTC Controls.

The libraries are templated onto Ion Sphere Particles (ISP, which are proprietary beads) using the Ion OneTouch Template Kit and OneTouch instrument. Templated beads are enriched from un-templated beads on the OneTouch ES, and loaded onto the 318 chip with reagents to allow the sequencing reactions to take place.

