The Ion PGM Sequencer uses the reagents provided in the Ion PGM Sequencing Kit to detect nucleotide incorporation on the chip. The signal generated by the sequencing reaction on the 318 chip is translated into base calls and then reads. The DNA reads are 'mapped' to the reference human genome (hg19) followed by detection of SNVs, Indels, and CNVs.

The RNA reads are 'mapped' to a reference containing control sequences and candidate gene fusion sequences. Gene fusions are detected as present if they map to these sequences and pass certain filtering criteria.

The end result of this workflow is a set of variant calls that correspond to the original sample. The Ion PGM Torrent Suite software will call out any variation between the Reproducibility Sample member sequence at the locations designated in the Hot Spot file. This process is executed using the Ion PGM Torrent Suite software which runs on the Ion Torrent Server. The Ion PGM Torrent Suite software manages the complete end-to-end workflow from sample to variant call.

The clinical data will be recorded in an electronic case report form (eCRF) managed digitally in the platform Medsharing. This system allows tracking and controlling the clinical

information associated to the specimen. It is based in an online interface that allows the centralized management of multiple clinical sites.

Study population

The study population includes all patients who satisfy all inclusion and do not present any of the exclusion criteria detailed in the protocol.

Inclusion Criteria (according with amendment 2, 23 November 2017)

- 1. Men or women 18 years of age or older.*
- 2. Patients with a diagnosis of non-small cell carcinoma (NSCLC) histologically or cytologically tested.*
- 3. When a blood sample is donated, the individual must have an active tumor, i.e. the patient has a tumor in the moment of blood collection. The diagnosed is based on image test i.e.: X- RAY, Ct SCAN, RMN, PET Scan and among other, and biopsy (liquid or standard).*
- 4. Informed consent form, signed and dated, stating that the patient (or the legal representative) has been informed of all relevant aspects of the clinical study before being incorporated into the study, when appropriate.*
- 5. Patients must give consent for the research use of their tissues on file or fresh or 2 tubes of blood if available, or both.*

Exclusion criteria

Patients who meet some of the following criteria will not be included in the study:

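### SAP section 7 handles inadequate DNA inconsistently when deciding which samples enter the primary ALK analysis, although the ALK call is made from RNA

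*SAP*

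**What the plan says.** Four statements in SAP section 7 bear on the matter.

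- Under the sequencing heading, for insufficient samples: "If at least 20 ug of DNA and 20 ug RNA or both are not obtained, the sample is eliminated from the primary analysis".
- Under the bioinformatics heading, for DNA: "DNA sample fails in QC parameters, it is eliminated from DNA dependent analysis, but it is included in primary analysis".
- In the same list, for RNA: "RNA sample fails in QC parameters, primary analysis is eliminated".
- A closing starred bullet raises, as a question, what to do with defective samples that could still answer the primary analysis. It replies: "Remove from the primary analysis, but group in special cases to analyze later".

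SAP 2.1.2 describes what each nucleic acid is used for. DNA reads are aligned to the human genome, "followed by detection of SNVs, Indels, and CNVs". For fusions, "The RNA reads are 'mapped' to a reference containing control sequences and candidate gene fusion sequences", and "Gene fusions are detected as present if they map to these sequences and pass certain filtering criteria". DNA and RNA go into separate libraries. SAP section 6 makes the NGS and Ventana results for ALK the primary endpoint; ROS1 appears only among the other endpoints in 6.3.

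**The concern.** The quality-control bullets treat DNA as irrelevant to the primary endpoint and RNA as decisive, which agrees with the assay description. The yield bullet makes DNA quantity a condition of entry to the same analysis and gives no reason. A sample with enough good RNA to give an ALK call is then left out because its DNA is scarce. The starred bullet adds a second difficulty: a sample with failed DNA and sound RNA fits its description of defective but answerable, yet the DNA bullet has already put that sample in.

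Sensitivity, specificity, positive and negative agreement, McNemar's test and kappa (SAP 8.1) are all computed on whatever set these rules leave. ALK positives are the scarce part of it, at an expected prevalence of 3-5%, so the set should be defined once and on grounds that relate to the ALK call.

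**Working it through.** The plan states no figure for this point, so there is nothing to reproduce. The check is mainly one of logic.

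**Step 1: the rules side by side.** Let DNA yield, RNA yield, DNA QC and RNA QC each be adequate or not, which gives 16 combinations. RNA passes QC in 8 of them. Read the yield bullet as excluding when either quantity is short. It then excludes 6 of those 8, while the QC bullets give no ground to exclude any. Four of the 6 are short of RNA, which is a relevant ground. The other two are short of DNA only. The four combinations in which RNA is adequate in both yield and quality are:

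| DNA yield | DNA QC | Yield bullet | QC bullets | Starred bullet |
|---|---|---|---|---|
| adequate | pass | in | in | not engaged |
| adequate | fail | in | in, expressly | out, if it counts as defective |
| short | pass | out | no ground to exclude | unclear |
| short | fail | out | in, expressly | out, if it counts as defective |

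Only the first row gets one clear answer.

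**Step 2: other readings.**
- *Staged (yield first, QC only for samples that pass).* Rows 3 and 4 are simply out. The direct clash in row 4 goes, but both rows still lose a sample with usable RNA. Row 2 is unaffected.
- *Yield bullet excludes only when both quantities are short.* Rows 3 and 4 pass the yield gate. Row 2 still conflicts with the starred bullet, and row 4 now does too.

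**Step 3: scale, for illustration.** The share of samples short of DNA only is not given; assume 10%, with 30% as a high case. The inputs are 120 ALK-positive tumours and the Wilson interval (both protocol 7.4) and a sensitivity of 0.80 (the SAP 8.1 cut-off). With z = 1.96,

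half-width = z × √[p(1−p)/n + z²/(4n²)] / (1 + z²/n)

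- n = 120: 1.96 × √(0.001333 + 0.000067) / 1.0320 = 0.071
- n = 108 (10% lost): 1.96 × √(0.001481 + 0.000082) / 1.0356 = 0.075
- n = 84 (30% lost): 1.96 × √(0.001905 + 0.000136) / 1.0457 = 0.085

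If 120 evaluable positives were kept as the target instead, a 10% loss would need 120/0.9 = 134 positives. At 5% to 3% prevalence, the number screened would rise from 2,400-4,000 to 2,667-4,445.

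**Step 4: the 20 ug threshold.** SAP 2.1.2 uses 5-micron sections and says "Two sections will be extracted in order to meet minimum tissue input requirements". Assume 6.6 pg DNA per cell, a tissue area of 10-200 mm² and 100,000 to 1,000,000 cells per mm³; none of these is in the documents. Two sections are 0.010 mm thick together, so the volume is 0.1-2 mm³.

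- Low end: 0.1 × 100,000 × 6.6 pg = 0.066 ug
- High end: 2 × 1,000,000 × 6.6 pg = 13.2 ug

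Under these assumptions even the high end is below 20 ug. Step 3 supposes a threshold that most samples can meet, so steps 3 and 4 do not describe the same rule.

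**The case against.** The strongest reply is that the bullets act at different stages. The yield bullet sits under sequencing and sends its data to pre-analytical quality control; the DNA and RNA QC bullets sit under bioinformatics. In that order a low-yield sample has already left, and the later bullets govern only what remains. This stands as a workable reading, although the SAP does not state it. A reader might infer that the rules flatly contradict each other and that any affected sample can be in or out at will; the documents do not support that. Staging does not explain why low DNA should bar a call made from RNA, and it does not settle the starred bullet.

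The yield sentence is also badly worded and might mean exclusion only when both quantities are short. The phrase about both fits that poorly, since it implies that one shortfall is enough, but the ambiguity is real.

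A reader might further infer that small biopsies are lost first, so that the agreement estimates are biased, or that the analyst can pick a rule after seeing results. Neither is documented. No link is given between DNA yield and NGS-Ventana agreement, and yield would ordinarily be known before sequencing. Both nucleic acids come from the same processed tissue, so a shortfall in DNA alone could be uncommon. Nor are the samples necessarily discarded for good, because the starred bullet sets defective ones aside for later analysis. Finally, 120 is the number to be analysed, the protocol abstract extends screening if it is not reached, and SAP 8.1 recalculates the sample size at each interim, so a loss might be replaced.

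**Conclusion.** The point holds as one of inconsistent handling. On the natural reading, the yield bullet excludes samples with adequate RNA from an RNA-based ALK analysis, while a neighbouring bullet treats failed DNA as no bar. The starred bullet conflicts with the DNA QC bullet on every reading considered, provided that a DNA failure counts as a defect. The first part depends on taking a shortfall in one nucleic acid as sufficient for exclusion; it survives the staged reading but not the reading that requires both to be short.

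The size cannot be derived from the documents. The change in half-width from 0.071 to 0.075 is an illustration under an assumed 10% loss and is small. It would be wrong to infer that the 20 ug rule in fact removed nearly every sample: that calculation rests on assumed areas and cell densities, and the NGS procedure is not available here. It justifies checking the quantity and unit, no more.

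**What to change.** Replace the insufficient-sample bullet with: *A sample is excluded from the primary ALK concordance analysis only if RNA input is below the assay minimum, RNA fails QC, or no RNA BAM file is generated; insufficient or failed DNA excludes it from DNA-dependent analyses only.* Naming the RNA file matters, because the present BAM bullet does not say which file it means.

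- Apply the same RNA-based rule to the separate ROS1 analysis, without moving ROS1 into the primary endpoint.
- Close the question in the starred bullet and align it with this rule.
- Report exclusions by reason and by Ventana ALK status, so that the actual loss can be seen.
- Check the 20 ug quantity and unit against the NGS procedure listed in protocol Appendix 1.

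The cost is SAP wording and re-inclusion of affected samples that already have RNA sequencing data. SAP version 2.0 is dated 10 July 2019, after the planned end of data collection on 30 June 2019, so samples never sequenced would not be recovered by new wording.

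### SAP 7 is inconsistent on whether a sample short only of DNA enters the primary ALK analysis, although the ALK fusion is called from RNA

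*SAP*

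**What the plan says.** The primary endpoint in SAP 6 is the ALK result by NGS and by Ventana. SAP 2.1.2 describes how NGS produces that result. On the RNA side, "The RNA reads are 'mapped' to a reference containing control sequences and candidate gene fusion sequences". The calling rule rests on that mapping: "Gene fusions are detected as present if they map to these sequences and pass certain filtering criteria". The DNA reads are mapped to the human reference genome, and their stated use is different: "followed by detection of SNVs, Indels, and CNVs". DNA is given no part in the fusion call.

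SAP 7 then sets several rules on who stays in the primary analysis:

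- The rule on low yield reads: "If at least 20 ug of DNA and 20 ug RNA or both are not obtained, the sample is eliminated from the primary analysis". What remains of these samples has another purpose: "The data will be used to establish pre-analytical QC parametric".
- The rule on DNA QC reads: "DNA sample fails in QC parameters, it is eliminated from DNA dependent analysis, but it is included in primary analysis".
- The rule on RNA QC reads: "RNA sample fails in QC parameters, primary analysis is eliminated".
- BAM files: a sample without them leaves the primary analysis. The rule does not say whether the DNA file, the RNA file or both are meant.
- A closing bullet covers defective samples that could still answer the primary question, and its instruction is: "Remove from the primary analysis, but group in special cases to analyze later".

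**The concern.** The two QC rules follow the assay: the ALK call needs RNA, so an RNA failure matters and a DNA failure does not. The insufficient-sample rule, read naturally, does not follow it. Two samples with equally good RNA are handled in opposite ways, depending on whether the DNA was too little or was enough but failed QC.

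At stake is the composition of the primary analysis set. ALK positives are scarce (3-5% prevalence in Protocol 7.4, with 120 expected), and the sample-size formulas in SAP 8.1 make no allowance for exclusions. Each evaluable positive pair removed for a DNA reason costs precision on sensitivity. Because the sentence can be read in two ways, and the closing bullet pulls against the DNA QC rule, two analysts could also build different primary sets from the same data.

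**Working it through.** **Step 1: the rules side by side.** The plan states no figure on this point, so there is none to reproduce. The check is one of logic. The 20 ug amounts are taken as printed; the argument does not depend on their size or unit.

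| RNA | DNA | Rule | Read as: either one short | Read as: both short |
|---|---|---|---|---|
| adequate | short | insufficient sample | out | in |
| adequate | enough, fails QC | DNA QC | in | in |
| short | adequate | insufficient sample | out | passes this rule |
| short | short | insufficient sample | out | out |
| fails QC | any | RNA QC | out | out |

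On the first reading, rows 1 and 2 have the same usable input for a fusion call and opposite outcomes. On the second, row 3 passes although it lacks the input that the call needs; a later RNA check might still remove it, but this rule does not. The sentence therefore needs rewriting on either reading.

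**Step 2: size, as illustration only.** Inputs: 120 ALK positives (Protocol 7.4); Wilson 95% interval (the method cited in Protocol 7.4); sensitivity p = 0.80 (the cut-off in SAP 8.1); share d of samples with short DNA but adequate RNA, which the documents do not give and which is assumed here to be 5%, 10% or 20%.

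Remaining positives: n = 120 × (1 − d).

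Wilson half-width: h = z × √[p(1−p)/n + z²/(4n²)] / (1 + z²/n), with z = 1.96.

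For n = 120: √(0.16/120 + 3.84/57,600) = √0.001400 = 0.0374; 1.96 × 0.0374 = 0.0733; divided by 1.032 this gives h = 0.071 (interval 0.720 to 0.862).

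| d (assumed) | positives lost | n left | half-width |
|---|---|---|---|
| 0 | 0 | 120 | 0.0711 |
| 5% | 6 | 114 | 0.0729 |
| 10% | 12 | 108 | 0.0748 |
| 20% | 24 | 96 | 0.0793 |

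Replacing the loss by further screening would take 3000/(1 − d) patients in place of 3000: 3158, 3334 or 3750.

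**Step 3: bias.** If sensitivity differs between the removed samples and the rest, the estimate is overstated by d × (sensitivity in the rest − sensitivity in those removed). With an assumed 0.80 in the rest and 0.70 in those removed, this is 0.005, 0.01 or 0.02 for the three values of d. With equal sensitivity it is zero. The documents give neither value.

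**The case against.** The strongest reply is that the two rules belong to different stages. The insufficient-sample rule concerns extraction yield, before sequencing; the QC rules apply afterwards, when a result may exist. SAP 2 describes an assay that handles DNA and RNA together, SAP 2.1.2 prepares one library of each per sample, and SAP 7 refers to samples that are not in the sequencing flow. If a DNA-short sample is never sequenced, it has no NGS result and its removal is ordinary handling of missing data. This stands as a limit: the point applies only to samples that have an RNA result. It does not rescue the sentence, which does not state such a condition.

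Two stronger readings are tempting. A reader might infer that valid ALK results are thrown away. The documents do not support that: no section says that DNA-short samples receive an ALK call, insufficient samples feed the pre-analytical QC work, and the closing bullet keeps answerable samples for later analysis. That bullet nonetheless confirms that they leave the primary analysis.

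A reader might also infer that sensitivity is inflated. DNA and RNA come from the same sections, so low DNA could mark scant tissue. But the samples in question have adequate RNA by definition, and nothing in the documents links DNA yield to NGS-Ventana agreement.

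Finally, 120 is the number of positives to be analysed, screening may extend to 6000, and sample size is recalculated at each interim analysis. Within that cap, lost positives could be replaced. This also stands, and it reduces the expected cost.

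**Conclusion.** The inconsistency is established from the text. SAP 7 applies RNA-only logic at the QC step and, on the natural reading, abandons it at the yield step; the alternative reading fails in the other direction. Its practical effect is that any sample with short DNA, adequate RNA and an RNA result is moved out of the primary analysis for a reason that does not bear on the ALK call.

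The size is unknown. Under the assumed 5% to 20%, the loss of precision is modest: less than 0.01 on the half-width even at 20%. If no DNA-short sample was sequenced, no evaluable pair is lost and what remains is a matter of wording. Bias in sensitivity is conditional on a relation that the documents do not show. The case for a change rests on having one unambiguous primary set that matches the assay, more than on the numbers.

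**What to change.** Replace the insufficient-sample and BAM rules for the primary ALK analysis with a single RNA-based rule, for example: *A sample is removed from the primary ALK analysis if the minimum RNA input is not obtained, no RNA BAM file is generated, or RNA QC fails. A sample short of DNA or failing DNA QC is removed from DNA-dependent analyses only.*

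Align the closing special-cases bullet with this, so that it no longer removes samples that the rule keeps. Report the number excluded for each reason, separately for Ventana-positive and Ventana-negative patients, and add a sensitivity analysis under the rule as it now stands in SAP 7.

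Apply the rule to samples that already have an RNA result. New libraries for unsequenced samples are not part of the change: SAP version 2.0 (10 July 2019) postdates the planned end of data collection (30 June 2019), and such runs would be extra laboratory work. The cost is a short edit to SAP 7, slightly more analysis, and some samples in the primary set without DNA data.

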2 RESPONSIBLE PARTIES

The Precision Medicine Center of Excellence of Pfizer Chile (CEMP in Spanish), based in Santiago, Chile will be responsible for the execution of the non-interventional protocol.

The mission of the Center (CEMP) is to deliver technical and operational excellence in Precision Medicine R&D and molecular diagnostic development in Latin America for the benefit of cancer patients all over the world.

The other involved parties will be the hospital Centers that will be providing samples, the diagnostics test providers (Vysis ALK Break Apart FISH or Ventana ALK IHC) and the sequencing providers both in Chile and Brazil.

Their main responsibilities will be the following:

CEMP, through CRO ICON, will be responsible for sample collection and transportation from hospital centers to the FISH/Ventana ALK test providers, the sequencing providers and/or CEMP facilities. Thus, CEMP will receive clinical data informed consents, tissue and blood samples coming from hospitals, and data results of FISH/Ventana ALK and NGS from research centers.

In Brazil, AC Camargo Cancer Center (ACC), as a FISH/Ventana ALK and NGS sequencing provider, will perform nucleic acid extraction from both kind of samples (tissue and blood). ACC will also perform genomic analysis using a PGM device. Biondata (.vcf and .pdf files) coming from the sequencers will be processed and raw data will be supported in a Data Center. ACC will be responsible for the storage of the remaining tissue and the nucleic acid from blood in Brazil.

In Chile, CEMP Genomic Laboratory and the sequencing center Genoma Mayor will perform nucleic acid extraction from both kind of samples (tissue and blood). Also, they will perform genomic analysis using a PGM device and process the biondata coming from the sequencers and will store the raw and processed data accordingly. CEMP will be responsible for the storage of the remaining tissue and the nucleic acid from blood in Chile.

In both countries, the NGS service providers (ACC, Genoma Mayor and Genomic Laboratory at Pfizer) will work as a parallel sequencing facility.

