8.2 Patient withdrawal

Patients may be withdrawn at any time at the discretion of the investigator or sponsor for safety, behavioral, or administrative reasons. In any circumstance, every effort should be made to document subject outcome, if possible. The investigator should inquire about the reason for withdrawal and follow-up with the subject regarding any unresolved adverse events.

If the patient withdraws from the study, and also withdraws consent for disclosure of future information, no further evaluations should be performed, and no additional data should be collected. The sponsor may retain and continue to use any data collected if no withdrawal of consent is requested.

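### An unfinished note in SAP section 7 removes answerable 'defective' samples from the primary analysis under undefined criteria, with no blinding stated

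*SAP*

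**What the plan says.** SAP section 7 sets out which samples leave the primary analysis. Those without an ALK reference result, with too little nucleic acid, or without a BAM file are removed. Two QC rules follow. For DNA: "DNA sample fails in QC parameters, it is eliminated from DNA dependent analysis, but it is included in primary analysis". For RNA: "RNA sample fails in QC parameters, primary analysis is eliminated". No limit for the QC parameters is given with either rule.

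The list ends with a question, "There are special cases where the primary analysis could be answered with defective samples, should it continue", and an instruction, "Remove from the primary analysis, but group in special cases to analyze later".

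SAP section 5.1 defines the full analysis set by eligibility alone and does not mention these removals. SAP section 8.2 lists only prevalence and ALK concordance, so the later analysis of special cases is not described. Protocol section 2 says that the sponsor's centre will receive "data results of FISH/Ventana ALK and NGS from research centers".

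**The concern.** The closing note covers samples that are in some way defective but could still answer the primary question. To recognise such a sample, someone has to judge whether an ALK answer can be had from it. The SAP does not say what counts as a defect, who decides, when, or without sight of which result. The sponsor's centre holds both halves of each pair, so that judgement could be made by someone who knows whether the pair agrees.

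A discordant pair invites a search for a technical explanation and a concordant pair does not. If removals follow that pattern, the discordant cells of the two-by-two table shrink and the concordant cells do not. PPA, NPA and kappa then rise with no change in the assay. These are the agreement measures named in SAP section 8.1, and positives are few, so each removed false negative counts.

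**Working it through.** **1. The rules side by side.**

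| Situation | Rule in SAP section 7 | Criterion given |
|---|---|---|
| Too little DNA or RNA | Out of primary analysis | Yes, a quantity |
| No BAM file | Out | Yes, present or absent |
| DNA fails QC | Stays in | No threshold |
| RNA fails QC | Out | No threshold |
| Defective but answerable | Out, analysed later | None |

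Fusions are called from RNA reads (SAP section 2.1.2), so a sample with failed DNA and sound RNA can still answer the ALK question. The third row keeps it and the fifth row, as worded, removes it. For RNA, the line between pass and fail is not fixed in advance.

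**2. The planned denominator.** The protocol abstract and section 7.4 plan for 120 ALK positives. At 3,000 samples and the midpoint of the stated 3-5% prevalence, 3,000 x 0.04 = 120, so the figure reproduces. The remaining 3,000 - 120 = 2,880 samples are reference-negative.

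**3. Effect on PPA.** PPA = TP / (TP + FN). The 12 false negatives and the numbers removed are assumptions; the documents give neither. Intervals are 95% Wilson, the method named in protocol section 7.4.

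| False negatives removed | PPA | 95% interval |
|---|---|---|
| 0 | 108/120 = 90.0% | 83.3-94.2% |
| 3 | 108/117 = 92.3% | 86.0-95.9% |
| 6 | 108/114 = 94.7% | 89.0-97.6% |
| 9 | 108/111 = 97.3% | 92.4-99.1% |

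The gain is 2.3, 4.7 or 7.3 points.

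**4. Effect on NPA.** NPA = TN / (TN + FP). Assume 30 false positives among the 2,880 negatives: 2,850/2,880 = 98.96%. Removing 9 of them gives 2,850/2,871 = 99.27%, a gain of 0.3 points.

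**5. Effect on kappa.** Use TP 108, FP 30, FN 12, TN 2,850, with chance agreement from the products of the margins.
- All samples kept: Po = 2,958/3,000 = 0.9860; Pe = (138 x 120 + 2,862 x 2,880)/3,000² = 0.9177; kappa = 0.0683/0.0823 = 0.830.
- Six false negatives removed: Po = 2,958/2,994 = 0.9880; Pe = (138 x 114 + 2,856 x 2,880)/2,994² = 0.9193; kappa = 0.851.

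**6. Comparison case.** If 5% of positives are removed regardless of result, the expected table is 102.6/114, still 90.0%, and the interval is about as wide (83.1-94.3%). The bias comes only from a link between removal and discordance.

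**The case against.** The strongest reply is that the question is not open. The next sentence orders removal, and on its face the order applies to every such sample. Coming straight after the input, BAM and RNA-QC rules, it may mean only that a sample failing one of them stays out even if a call could be read. That would prevent rescue of failed samples because their calls look useful, and so would narrow result-dependent choice. This is a fair reading, and if it is intended, one sentence would settle it. But the note does not limit itself to samples failing those rules, its wording also reaches the DNA failures that the SAP keeps, and the RNA rule has no threshold to make removal uniform.

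It is also fair that the SAP says the analysis could be answered, not that a valid call exists or that anyone compares it with the reference before deciding. Much of the NGS work is done by external centres, and protocol section 2 does not say who assigns QC status.

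Two stronger readings are tempting and should not be drawn. The first is that withdrawal is another way to remove discordant pairs, because "Patients may be withdrawn at any time at the discretion of the investigator or sponsor for safety, behavioral, or administrative reasons". Protocol section 8.2 also says "The sponsor may retain and continue to use any data collected if no withdrawal of consent is requested". Neither document removes a withdrawn patient's collected result from the analysis, and withdrawal is not among the removals in SAP section 7. The second is that such exclusions would change the conclusion about NGS. From 90.0% the lower limit is already 83.3%, above the 0.8 sensitivity cut-off in SAP section 8.1, which is given for sample sizing. Crossing 0.8 needs a lower assumed start, for example 92/120 = 76.7% becoming 92/114 = 80.7%.

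**Conclusion.** The point holds as a gap in the exclusion rules. The SAP directs removal of an undefined class of answerable samples, conflicts with its own DNA rule, sets no RNA-QC limit and states no blinding, while one party receives both results. The text permits result-linked exclusion; nothing in it shows that this was planned or took place.

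The size rests on assumed counts. With 120 reference positives and 12 false negatives, selective removal of 3 to 9 would add about 2 to 7 points to PPA. The effect on NPA is far smaller because negatives are many. If removals are unrelated to the result, the expected PPA does not move. No documented threshold is crossed from a 90% start.

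**What to change.** In SAP section 7:

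- Delete the special-cases note.
- State that, once both tests have been attempted, a sample leaves the primary analysis only under the input-quantity, no-BAM or RNA-QC rule. Add a numeric RNA-QC threshold, since none is given now.
- Confirm that DNA-QC failures stay in, as the existing rule says. The existing removal of patients without ALK data is unaffected.
- Have QC status assigned by staff blind to the Ventana/FISH result, and before the two results are joined. Keep every sample that passes, whatever its call.
- Tabulate exclusions by reference result, and by NGS/reference cell where a call exists.
- Add a sensitivity analysis that restores excluded samples with a readable ALK call.

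The cost is a few sentences, one threshold to agree, a table and one rerun. Some lower-quality samples will stay in, so reported agreement may be slightly lower.
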